	15.2 Turtle Bedside Log	
	15.3 Turtle Rehab Assessment Log	

List of Abbreviations:

Apgar Appearance, Pulse, Grimace, Activity, and Respiration

BW birth weight

DR delivery room

g gram

IVH intraventricular hemorrhage

kg kilogram

LBW low birth weight

NICU neonatal intensive care unit

SAE serious adverse event

VLBW very low birth weight

WPH Winnie Palmer Hospital for Women and Babies

An Evaluation of Early Use of the Turtle Midliner and Intraventricular Hemorrhage (IVH) Outcomes in Premature Babies: A Randomized Controlled Trial

1. Research Synopsis

1.1 Study Title

An Evaluation of Early Use of the Turtle Midliner and Intraventricular Hemorrhage (IVH) Outcomes in Premature Babies: A Randomized Controlled Trial

1.2 Study Population

The study population will comprise inborn infants $\leq 30 \frac{6}{7}$ weeks gestational age undergoing inpatient care in the Neonatal Intensive Care Unit at Winnie Palmer Hospital for Women and Babies.

1.3 Study Design

This study is a single-site prospective randomized controlled clinical trial.

1.4 Sample Size

The investigators for the study at Winnie Palmer Hospital for Women and Babies (WPH) anticipate a total enrollment of 150 neonates with 75 in each group (75 in control group and 75 in treatment group).

1.5 Study Duration

The study duration is estimated to continue until July 30, 2020.

1.6 Primary Objective

The primary objective of this study is to determine if infants positioned with the Turtle Midliner to optimize midline head positioning will have a better IVH outcome, determined by a decrease in rate of occurrence or severity of IVH, when compared to infants receiving the standard care (control group) with no Turtle Midliner intervention.

1.7 Secondary Objectives

None.

2. Background and Significance

Intraventricular hemorrhage (IVH) is defined as bleeding into the ventricles of the premature infant brain-the highest risk for the lowest gestational ages. IVH almost always occurs between birth and the first 72 hours of life. The four grades of IVH are based on the degree of bleeding; the greater the severity of the bleed, the more likely to have a poor outcome. Complications can include hydrocephalus, mental retardation, cerebral palsy and seizures. Neurologic sequelae can lead to death. Even for low grade bleeds the studies show the negative effects on cognitive scores and an increased incidence of learning disabilities. In addition, these same children often suffer from attention deficit disorder and other behavioral dysfunctions, which require intervention in order for the child to successfully integrate into school and society.

The incidence of IVH in very low birth weight infants (1500g) has declined from 40-50% in the early 1980s to 20% in the late 1980s. However, in the last two decades the occurrence of IVH has remained stationary. In extremely premature infants weighing 500-750g, IVH occurs in about 45% of neonates (Philip, Allan, Tito, & Wheeler, 1989).

Since increased risk of IVH can be associated with changes of intracranial pressure, many medical protocols supported by the research efforts of Bedwell have established IVH bundles which are designed to help reduce fluctuations in intracranial pressure while managing the micro-preemie infant during the first few days of life (Bedwell, Bright, & Sekar, 2015).

The correlation between IVH and head positioning of the extremely low birth weight infants has now made its way into research literature. Malusky suggests that venous obstruction can result from increased external pressure on the venous system when the micro-preemie infant has their head positioned to the side rather than maintaining a neutral position (Malusky & Donze, 2011). With this in mind many neonatal intensive care units (NICUs) around the world have instituted practices which include strict neutral positioning often combined with raising the head of the bed for all infants <1500 grams during their first three-plus days of life.

Therefore, we are aiming to conduct a prospective randomized controlled trial in order to answer the research question: Does early use of the Turtle Midliner reduce the incidence and/or level of severity of intraventricular hemorrhage if used in infants born at $\leq 30 \frac{6}{7}$ weeks and neutral position is maintained for the first 72 hours of life? We hypothesize that the use of early consistent neutral positioning compared to the standard care (nested positioning) practiced in the NICU will reduce the risk of intraventricular hemorrhage in preterm infants born at $\leq 30 \frac{6}{7}$ weeks and have a positive effect on the incidence and/or level of severity of intraventricular hemorrhage in this population.

3. Objectives

3.1 Primary Objective

The prime objective is to determine if early application of the Turtle Midliner for preterm infants, ≤ 3 hours following birth and with subsequent continuous use through 72 hrs. of life to ensure maintenance of optimal midline positioning (treatment group), will impact the IVH outcome as determined by a reduction in the rate and/or severity of IVH when compared to infants receiving the standard regimen of care (control group).

3.2 Secondary Objectives

None

4. Study design/methodology

This study will be registered in Clinical Trials (clinicaltrials.gov) with the primary endpoint being a difference in IVH incidence and severity. We propose to conduct a randomized controlled trial in preterm infants (gestational age $\leq 30\ 6/7$ weeks) comparing the use of the Turtle Midliner and the standard of care practice (Control group). While blinding of study groups is always desirable in randomized studies, this will not be possible for this study.

Study Procedure

After eligibility of the infant is determined and the study informed consent is obtained from the parent or legal guardian, subjects will be randomized.

Randomization will follow a block randomization table that will determine if the infant will go into the group that will be positioned using the Turtle Midliner (Treatment Group) or not (Control Group).

All clinical care will be provided with consideration of the gestational age of the subject and follow NICU department guidelines and as ordered by physician and/or ARNP providers.

The key distinction for this study will be the use of the Turtle Midliner as a positioning aid in addition to standard of care for the Treatment Group, as opposed to solely standard practice of nesting and the use of rolls and other aids for the Control Group.

Treatment Group

The application and maintenance of the Turtle Midliner is within the scope of practice and skill-set of the NICU nursing and ancillary staff. The device has been in use in the WPH NICU since May 2016 when ordered by physician or nurse practitioner.

The use of the Turtle Midliner will be in addition to the NICU department process guidelines for positioning relevant to the gestational age of the subject. The Turtle Midliner will be applied no later than 3 hours following birth under the supervision of a

study investigator. The size/fit and application of the device will be according to the manufacturer's guidelines. The neutral midline head position, supine or slightly side-lying, with a bed elevation between 15° and 30° will be maintained during the first 72 hours of life. A member of the NICU physical therapy staff will perform and document a goniometry measurement (head/neck angle with head midline and perpendicular to shoulders, in line with the axial spine and not > than 5° deviation) a minimum of once daily during the first 72 hours of life and make any adjustments necessary, which is within their scope of practice.

Caregivers will document the NICU integrated flowsheet and the Sunrise electronic record with interventions regarding positioning, handling, skin assessment etc. per standard practice requirements.

The Turtle Midliner placement will be documented by clinical staff assigned to the subject's care every 2-4 hours on a tracking log. The active study period will end after the first 72 hours of life. The positioning device will be removed and the clinical care will continue according to NICU guidelines.

In the instance that phototherapy is ordered by the attending physician for babies in the treatment group, a compatible Turtle Midliner phototherapy eye shield will be used following manufacturer's size and guidelines.

Control Group

All clinical care for the control group will be within NICU department process guidelines relevant to the gestational age of the subject and as ordered by physician and/or ARNP providers. The neutral midline head position with the aid of nesting and/or rolls with a bed elevation between 15° and 30° will be maintained throughout position changes during the first 72 hours of life, which is standard practice. Caregivers will document the NICU integrated flowsheet and the Sunrise electronic record with interventions regarding positioning, handling, skin assessment etc. per standard practice requirements.

Data Collection

At Study Entry

Basic demographic information and delivery history will be collected.

Maternal Information- Only maternal information contained within the subject's record will be collected; the mother's record will not be accessed

Data collection will include: prenatal maternal conditions, maternal medications, mode of delivery, and delivery complications.

Clinical Data- collected from birth through the first 72 hours of life:

Procedures and conditions that may contribute to IVH will be collected, such as: sepsis (positive blood culture, vasopressors, steroids, bolus administrations (fluids/meds), hypoglycemia (serum glucose <45) or hyperglycemia (serum glucose >200), hypercarbia (CO₂ >65mmHg), apnea/bradycardic episodes requiring stimulation, patent ductus

arteriosus, maximum respiratory support, suction events, line placements (PICC, IV, UAC/UVC) and/or needle punctures, UAC/UVC line collections, chest tube insertion, and any other noxious event

The subjects in both groups meet criteria for a standard of care head ultrasound at 6-8 days of life. Results from the head ultrasound report will be captured.

Clinical Outcomes Data – collected through date of discharge

The results of the last head ultrasound and/or magnetic resonance imaging (MRI) of the brain before discharge will be collected if these additional tests were ordered during the hospitalization (as solely determined by the attending neonatologist and not for study purposes).

Outcome data will include: days on mechanical ventilation throughout hospital stay, discharged home with G-Tube, discharged home on respiratory support (FiO₂, mode/settings), discharged with shunt, and length of stay (# days).

Adverse Event/Serious Adverse Event

The device, Turtle Midliner, solely impacts the skin contact areas. Only adverse events related to skin breakdown requiring wound care consultation with treatment will be reported as an adverse event. The principal investigator will evaluate adverse events related to skin integrity.

Any death will be reported as a serious adverse event according to Orlando Health IRB policy.

Major Protocol Deviation

For the purpose of this study, the midline position will be maintained with consistent use of the Turtle Midliner for all randomized study subjects in the treatment group (Turtle group) from ≤ 3 hours to 72 hours from birth. If the device is not utilized for a period greater than 30 consecutive minutes, the situation will be evaluated by the principal investigator. A major protocol deviation will be reported if the device was not in place for any reason other than the safety or well-being of the subject.

Study Endpoint

The study period will be the first 72 hours of life with data collection for clinical outcomes to continue until discharge from the hospital, transfer to another institution, removal or withdrawal from the study, or death. There will be no additional contacts or follow-up for subjects beyond those time points.

The primary endpoint for the study is the difference in IVH incidence and severity between the two groups from birth through the first 72 hours of life.

5. Study Population

Each study subject must meet all of the indicated inclusion criteria and none of the exclusion criteria noted below:

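### The plan rules out blinding without excepting the head ultrasound reader, although the device is off before the scheduled scan and withholding the allocation from the reader would cost almost nothing

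*Combined protocol and SAP*

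**What the plan says.** - **Blinding.** Section 4 (Study design/methodology): "While blinding of study groups is always desirable in randomized studies, this will not be possible for this study". No role is named and none is excepted.
- **End of the visible intervention.** Section 4, Treatment Group: "The active study period will end after the first 72 hours of life", and then "The positioning device will be removed and the clinical care will continue according to NICU guidelines".
- **Scheduled outcome scan.** Section 4, Clinical Data: "The subjects in both groups meet criteria for a standard of care head ultrasound at 6-8 days of life". The data source is the routine report: "Results from the head ultrasound report will be captured".
- **Later imaging.** Section 4, Clinical Outcomes Data: "The results of the last head ultrasound and/or magnetic resonance imaging (MRI) of the brain before discharge will be collected", where such tests were ordered for care.
- **Charting.** Section 4, for both groups: "Caregivers will document the NICU integrated flowsheet and the Sunrise electronic record with interventions regarding positioning".
- **Primary endpoint.** Section 4, Study Endpoint: "The primary endpoint for the study is the difference in IVH incidence and severity between the two groups". Section 2 describes IVH as having four grades.

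Neither Section 4 nor the analysis plan in Section 7 says who grades the scan or whether that person is kept unaware of the arm.

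**The concern.** A visible head-positioning device makes it impossible to blind the people at the bedside. That reason does not extend to someone grading images acquired after the device has gone. The plan gives up blinding altogether, although its own schedule leaves room for it in the role that produces the primary endpoint.

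The endpoint rests on a person's judgement: whether a bleed is present and, if so, its grade. The objective counts a reduction in either rate or severity, so a shift between grades matters as well as a missed bleed. The arm could reach the reader through positioning entries in the electronic record or through the imaging request.

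Bedside care is unblinded and will stay so. The reading is the part of the primary result that can still be protected cheaply. Without a stated safeguard, a positive result is open to the objection that the reader may have known the arm.

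**Working it through.** **1. Is masked reading feasible on the plan's own schedule?** The device is removed after 72 hours. If day 1 is the first 24 hours, day 6 begins at 5 × 24 = 120 hours, which is 120 − 72 = 48 hours after removal. Counting the day of birth as day 0 lengthens the gap. At the scheduled scan the device is therefore no longer on the infant.

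**2. Reproducing the planned power.** Section 7 gives 71 per group, 80% power, a two-sided pooled Z test at 0.05, a 15% target rate with the device, and a 20% difference. Read as absolute, the control rate is 15% + 20% = 35%. With X control events and Y device events, n = 71 per group:

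Z = (X − Y)/n ÷ √[p̄(1 − p̄) × 2/n], where p̄ = (X + Y)/(2n); reject if |Z| > 1.96.

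Summing the binomial probabilities over all pairs (X, Y) that reject gives power of 80.4% at 71 per group and 79.7% at 70. The plan's 71 is reproduced, so the same test can be used below.

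**3. What one-sided misreading would do.** The documents give no misreading rates, so these are assumptions. There is no true effect, the true IVH rate is p in both arms, and the reader misses a share f of bleeds in the device arm only. The device arm is then read at p(1 − f), and the spurious benefit is p × f. The higher rate, 35%, is the control rate implied by Section 7; 20% is an assumed lower rate.

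| True IVH, both arms | Share missed, device arm | Device arm as read | Spurious benefit (points) | Two-sided rejection | Rejection favouring the device |
|---|---|---|---|---|---|
| 35% | 0 | 35.00% | 0 | 5.0% | 2.5% |
| 35% | 5% | 33.25% | 1.8 | 5.7% | 4.2% |
| 35% | 10% | 31.50% | 3.5 | 7.4% | 6.6% |
| 35% | 20% | 28.00% | 7.0 | 15.0% | 14.8% |
| 20% | 0 | 20.00% | 0 | 5.1% | 2.6% |
| 20% | 5% | 19.00% | 1.0 | 5.4% | 3.6% |
| 20% | 10% | 18.00% | 2.0 | 6.2% | 5.0% |
| 20% | 20% | 16.00% | 4.0 | 9.6% | 9.1% |

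**4. What masking aims for.** If the reader does not know the arm, misses should fall equally on both. With 10% or 20% missed in both arms, the rejection rate is 5.2% and 5.2% at 35% IVH, and 5.1% and 5.0% at 20% IVH. The harm comes from the difference in misreading between arms, not from misreading itself.

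**The case against.** The Section 4 sentence speaks of study groups. In a trial of a visible device it can fairly be read as describing caregivers and parents, with outcome assessment simply not mentioned. The scan is a routine clinical product made days after the device is removed, so the reader may well not know the arm in practice. Positioning entries are described in the same words for both groups, device placement goes on a separate tracking log, and Section 9 restricts access to case reports and subject records. Appendix 15.1 lists a separate head ultrasound sheet whose content cannot be seen. The misreading model is one-sided and binary, and its most striking figure needs one in five device-arm bleeds missed and none in control.

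Much of this is right as a limit on the claim. The sentence is not shown to be false, and the reader is not shown to be unmasked. The 15.0% is not a forecast; at 5% missed the effect is small. But on the narrower reading of the sentence the plan is still silent on who reads the scan and what that person knows. Section 9 does not clearly keep the reader out of the clinical chart, and positioning entries there could name the device.

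It is also true that *not told* is weaker than secure masking. A reader can open the chart, a person transcribing the report may know the arm, and a scan ordered for care before 72 hours could show the device. The later ultrasound or MRI matters here only if it is used for the IVH outcome. These points limit what the change achieves; they do not argue against making it.

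**Conclusion.** The concern holds. The plan rules out blinding, excepts no role, and leaves the reading of a graded primary endpoint unprotected, although its own timing allows masking. The change is worth making because it is cheap and guards the primary result; the omission does not invalidate the trial.

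The size depends on assumed misreading confined to one arm. With no true effect and 71 per group, 5% to 20% of device-arm bleeds missed would take the rejection rate to between 5.7% and 15.0% at 35% IVH, and to between 5.4% and 9.6% at 20% IVH. The 35% rests on reading the planned difference as absolute, which matches the stated power. The binary test does not capture shifts between grades. The data sheets and logs are listed by title only and could not be checked.

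**What to change.** Replace the blinding sentence in Section 4 with: *Caregivers cannot be blinded; the head ultrasound reader will not be told the allocation.* Then:

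- Keep the allocation off the ultrasound request.
- Apply the same rule to any later ultrasound or MRI used for the IVH outcome.
- Record the reported grade on a data sheet that does not carry the arm, and link it to allocation only at analysis. If the existing head ultrasound sheet already omits the arm, say so.

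If readers are already unaware of the arm in practice, the sentence simply records it and lets the trial claim it.

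**Cost.** One protocol sentence and an instruction for the request and the sheet. The sample size is unchanged (142, maximum 150), and no second reader, extra scan or procedure is needed. The documents give no costs, so calling this nearly free is a judgement. Masking remains imperfect if a reader opens the full chart, and bias from unblinded care, including the decision to order later imaging, is untouched.

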5.1 Inclusion Criteria

1. Gestational age less than or equal to 30 6/7 weeks at birth
2. Less than 3 hours from birth
3. Informed consent obtained from parent or legal guardian prior to reaching time point for randomization

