5.2 Exclusion Criteria

1. Presence of genetic/chromosomal abnormality, congenital hydrocephalus, congenital neuromuscular disorder, or other diagnosis determined to impact survival or generalizability of results
2. Unable to participate for any reason based on the decision of the principal investigator.
3. Infants born outside Winnie Palmer Hospital for Women and Babies

6. Study Duration/ Study Timeline

Projected start date approx. April 2018 following IRB approval)

- | | | |
|-----------|---|-----------|
| • Stage 1 | Enroll subjects following IRB approval through April 2020 | 24 months |
| • Stage 2 | Data analysis through July 2020 | 3 months |
| • Stage 3 | Poster, abstract and/or manuscript through January 2021 | 6 months |

7. Statistical Analysis Plan

Sample Size Determination:

A sample size of 142 neonates with 71 in each group (71 in control group and 71 in intervention group) was determined in order to achieve 80% power to detect a 20% difference in IVH between the two groups, using a target rate of IVH of 15% in the intervention group. The test statistic used was the two-sided Z test with pooled variance. The significance level of the test would be 0.05.

We aim to allow for an additional 5% in sample size to adjust for either voluntary or involuntary withdrawal of some of the enrolled subjects. Upon reaching 142 enrollees the data will be reviewed. If any baby (ies) within the first 142 enrollees was withdrawn, the baby will be replaced according to the original randomized group, up to an additional 8 babies to ensure the power of the study and maintain a balance between the groups. A maximum of 150 babies will be enrolled.

Data Analysis:

Data analysis will include descriptive statistics with means and proportions. Comparative statistics will be used to compare IVH outcomes in the two groups. IVH outcome will be

determined by a reduction in the rate and/or severity of IVH. Any additional information on data points may be described in tables and/or graphs.

8. Informed Consent Process

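### In an unblinded trial, randomised infants can leave the IVH comparison through undefined removal or involuntary withdrawal and be replaced, with no rule that keeps them in the analysis

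*Combined protocol and SAP*

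**What the plan says.** - **Blinding.** Section 4 says that blinding of the study groups is not possible.
- **End of data collection.** Section 4 (Study Endpoint) provides for "data collection for clinical outcomes to continue until discharge from the hospital, transfer to another institution, removal or withdrawal from the study, or death", with no contact or follow-up afterwards. Removal is listed separately from withdrawal, and neither is defined.
- **Withdrawal allowance.** Section 7 (Sample Size Determination) adds 5% to "adjust for either voluntary or involuntary withdrawal of some of the enrolled subjects". It does not say what makes a withdrawal involuntary.
- **Replacement.** The data are reviewed at 142 enrollees. Infants among those 142 who were withdrawn are replaced in the arm to which they were randomised, with at most 8 replacements and 150 infants in all. The stated purpose is to protect power and keep the arms balanced.
- **Outcome scan.** Section 4 (Data Collection) says that infants in both groups qualify for a standard-of-care head ultrasound at 6-8 days of life, and that its report is captured.
- **Analysis.** Section 7 (Data Analysis) says only that comparative statistics will be used on IVH outcomes in the two groups. It names no analysis population, intention-to-treat rule or method for missing outcomes.

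**The concern.** Randomisation protects the comparison only while the randomised infants stay in it. Here an infant can be taken out on unstated grounds by people who know the arm. Data collection then stops, and another infant fills the place.

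Timing makes this matter. Section 2 says that IVH almost always occurs within the first 72 hours, but the scan is at 6-8 days. An infant withdrawn between those points has usually already bled or not bled, and the result may never be recorded. If the reasons for leaving differ between arms, or follow the infant's clinical course, the remaining infants are no longer a fair comparison. A replacement restores the count but not the lost outcome.

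The loss is avoidable, because the scan is routine care and its result only has to be read from the chart.

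**Working it through.** **1. The plan's own figures.** Inputs from Section 7: 80% power, 15% IVH in the intervention arm and a 20% difference. The control rate is not stated. I read the difference as absolute, so 35% against 15%, because a relative 20% would need 1,565 to 2,036 infants per arm. The plan also says "The test statistic used was the two-sided Z test with pooled variance" and "The significance level of the test would be 0.05".

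n per arm = [1.96·√(2·0.25·0.75) + 0.842·√(0.35·0.65 + 0.15·0.85)]² / 0.20² = 72.4, so 73.

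The plan has 71. Power at 71 per arm is 0.792 by the normal formula and 0.804 by exact enumeration, so the plan's figure stands. The allowance also reproduces: 142 / 0.95 = 149.5, so 150, and 150 − 142 = 8. Eight is a cap on replacements; the plan sets no cap on removals.

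**2. Does a withdrawn infant leave the comparison?** The plan does not say so directly. If withdrawn infants stayed in the analysis, replacing them would not be needed to protect power. Their exclusion is therefore a strong implication of the replacement rule, and nothing in Section 7 contradicts it.

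**3. How much could it matter?** These are assumptions, not plan figures: no true effect, 71 per arm, the same IVH rate p in both arms, and p = 25% as the midpoint of 15% and 35%. In the device arm, k infants with IVH are removed and replaced by new infants at rate p. No control is removed. This is the worst direction.

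- Control count C ~ Bin(71, p).
- Device count D = X − r + Y, where X ~ Bin(71, p), r = min(k, X) and Y ~ Bin(r, p).
- Z = [(C − D)/71] / √[p̄(1 − p̄)·2/71], where p̄ = (C + D)/142.
- False-reduction rate = P(Z > 1.96), by exact enumeration.
- Spurious difference ≈ k(1 − p)/71. For k = 2 this is 2·0.75/71 = 2.1 points.

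| k (p = 25%) | False-reduction rate | Spurious difference |
|---|---|---|
| 0 | 2.6% | 0 |
| 1 | 3.8% | 1.1 points |
| 2 | 5.4% | 2.1 points |
| 4 | 10.1% | 4.2 points |

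For k = 2 the rate is 7.2% at p = 15% and 4.5% at p = 35%. For k = 4 it is 16.6% and 7.5%. If all eight replacements were for device-arm IVH cases, the rate at p = 25% would be 26.7%. That is an extreme, not an expectation.

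**4. The other end of the range.** If removals are unrelated to arm and outcome, the bias is nil. If four IVH cases are removed and replaced in each arm, the expected difference between arms is again zero.

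**The case against.** A reader might infer that the principal investigator, who knows the arm, can remove randomised infants, because one exclusion reads "Unable to participate for any reason based on the decision of the principal investigator" and another covers "or other diagnosis determined to impact survival or generalizability of results". The documents do not support that. Both are eligibility criteria in Section 5.2, and Section 4 settles eligibility before randomisation. No section says who may remove an infant.

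A reader might also see a removal trigger that exists only in the device arm. Entry requires "Less than 3 hours from birth", while "The Turtle Midliner will be applied no later than 3 hours following birth", and device non-use beyond 30 consecutive minutes goes to the principal investigator. The stated consequence of non-use is evaluation and possibly a major deviation report. No removal follows from it, or from missing the application limit.

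Nor does the review at 142 enrollees show that withdrawals are decided with scan results in view. It replaces infants who have already been withdrawn.

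Two further objections carry weight. First, the stop rule concerns clinical outcomes, and Section 4 lists those under a separate heading after the 6-8 day scan. The rule may not end capture of that scan, and a result recorded before withdrawal is nowhere said to be discarded. Second, an infant withdrawn before the scan would usually have no study result for anyone to act on, so outcome-linked removal would have to work through clinical course. Both limit the likely size of the bias.

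What they do not remove is the combination of undefined involuntary withdrawal, open allocation, replacement, and no rule that keeps the withdrawn infant in the analysis.

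**Conclusion.** The point holds as a gap in the primary comparison that is cheap to close. Unblinded allocation, data collection ending at removal or withdrawal, and replacement in the same arm are stated rules. Exclusion of withdrawn infants from the IVH analysis is implied by replacement, and loss of the 6-8 day result is possible but not stated.

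The realised bias is unknown and may be nil. Under the assumed worst direction at 25% IVH, one to four selective replacements would produce a spurious difference of 1.1 to 4.2 points, against a design target of 20. The chance of a false reduction would rise from 2.6% to between 3.8% and 10.1%. These figures show sensitivity to a few infants and do not predict what will happen.

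**What to change.** 1. **Section 4, Study Endpoint.** Delete removal as an end of data collection. State that the standard-of-care 6-8 day head ultrasound result is captured for every randomised infant unless a parent withdraws consent for data use.
2. **Section 7.** State that the primary IVH comparison includes all randomised infants in their assigned group. Limit the term withdrawn to withdrawal of parental consent for data use. Make any extra infants, up to the maximum of 150, additions to the randomised total and not substitutes.

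With these two changes, the eligibility wording and the 3-hour limits need no alteration for this point. Infants who die or are transferred before the scan need their own rule, which this change does not supply.

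**Cost.** Wording only, because the scan is already part of routine care. Planned power is kept: about 0.80 at 71 per arm and 0.81 at 75. The downside is that a few infants with late-diagnosed conditions or little device exposure stay in the analysis and slightly dilute the effect.
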